## **Introduction**

Acute gastroenteritis is one of the most frequent reasons for pediatric emergency consultations over the year, creating an important healthcare spending (1) in a disease which is auto-limited and has a favourable course in the majority of cases.

In this context of high volume of patients, it is very important to define which information is given to patients' caregivers about management, evolution and prognosis in this disease. A good discharge education in these patients can help families to feel ready to care after the patient at home. However, a bad comprehension of the information given, or an inadequate set of discharge instructions can lead to a worse therapeutic adherence and problems with follow up of this patients (2). Discharge instructions in emergency departments are not always adequate and are frequently unadapted to caregivers' level of comprehension, as it has already been described in previous articles (2). Evidence says that, in many cases, this leads to higher rates of unnecessary subsequent visits to emergency departments (3), and worse perceived satisfaction (4)

Video discharge instructions (VDI) have been evaluated in various studies, both in adults (5) and in pediatric populations, in which the aim is to improve the knowledge of caregivers, the comprehension of the information and the caregivers' satisfaction (6) when adding this resource to the usual verbal recommendations. These studies have shown that the efficacy of these videos is higher when they are brief, since it keeps the attention of the viewers focused in the important part of the message. Also, it has been suggested that in the future these instructions could be added to usual clinical practice as another element of patient-physician communication and as a way of educating patients and caregivers (6,7)

Our study tries to evaluate if it is possible to improve the quality of the information given to caregivers by adding a set of video discharge instructions to the usual verbal information given at discharge in patients who are diagnosed of acute gastroenteritis in pediatric emergency departments. Our hypothesis is that associating video discharge instructions to usual verbal instructions, the comprehension will be better and the satisfaction with the information received will be higher).

The aims of this study are:

- The main aim is to compare the gained knowledge between a group of patients informed through the usual procedure and a group in which video discharge instructions are added.
- Secondary aims will be comparing between these two groups the level of satisfaction with the information received, and the rates of subsequent visits to emergency department and outpatient clinics.

## **Methods**

The study is designed as an open-label, parallel, randomized trial which takes place between June 2019 and June 2020 in the pediatric emergency department (PED) of a third-level Spanish hospital which receives 58000 emergencies annually

Population of study will be patients attending the emergency department who are diagnosed of acute gastroenteritis. ESPGHAN criteria for AGE will be used: decreased stool consistency and/or increased evacuation frequency during a period <7 days, associated or not to fever or vomiting(6). Patients are eligible if they are accompanied by a usual caregiver; if two caregivers were present, they would decide who would participate.

### Inclusion criteria

- Age between 1 month and 16 years.
- Visit to emergency department accompanied by usual caregivers.
- Ability to fluently communicate in Spanish
- Diagnosed of acute gastroenteritis and discharged home

### Exclusion criteria

- Severe dehydration
- Chronic comorbidities needing special instructions (neurologic, respiratory or cardiologic)
- Caregivers were not able to communicate in Spanish
- Patients finally admitted for hospitalization.

Sampling will be performed by enrolling a maximum of 3 patients every working shift (the first three who consult for diarrhea/vomiting and finally get AGE diagnosis). Enrollment will be performed by 4 different investigators of the study. The sample size is calculated to provide a statistical power of 80% at an alpha level of 5% to detect a two-tailed difference of 0.5 points between the two groups, difference which we consider clinically relevant. We calculated that with an estimated loss rate of 15% of patients between randomization and follow-up test, assuming a 1-point variance in test results based on previous studies[7], this statistical power would be reached by enrolling 75 patients in each group. Sample size has been calculated with STATA statistical software.

Patients will fill in an initial test evaluating their knowledge about acute gastroenteritis, prior to their discharge (test 1). They were then randomly assigned to the control or intervention group. In the first group of subjects (control group) caregivers will receive, after completing the test and prior to discharge, the usual verbal information and recommendations about AGE following the guidelines of the Spanish Society of Pediatric Emergencies In the second group (intervention group) patients will be shown a short 2-minute video providing the same information about AGE, in addition to verbal instructions. In both groups, instructions will be given by one of the main investigators in order to provide homogeneous and consistent information. Both sets of instructions explicitly include the information that had been previously asked in the test. All patients additionally received a discharge report which includes instructions concerning aftercare treatment.

After discharge, all caregivers will be contacted by telephone and were asked the same 5 questions from the initial test. The questionnaire must be completed by the same caregiver as in Step 1. This test also includes questions about subsequent visits to either emergency units or outpatient pediatric clinics, satisfaction with the information (caregivers were asked to evaluate information in a score 0-10) and a question about whether they perceive video instructions as potentially useful tool or not. All questions

will be asked to all patients independently of the group they are allocated to. The first telephonic contact will be established 72 hours after discharge. If investigators are not able to contact them at first, telephonic contact will be repeated every 1-2 days up to a total of 5 days before excluding them and considering them as lost in follow-up.

Simple, 1:1 randomization is performed using R software. Patients will be randomly assigned to a group by opening sequentially numbered paper envelopes which contain the group in which the patient would be allocated, ensuring thus allocation concealment. The trial will be open-label because of the characteristics of the interventions, which do not make masking possible.

The primary efficacy endpoint will be the difference between the score obtained in the initial test and the follow-up test. Secondary efficacy assessments include the number of caregivers who get a 5-point score in the follow-up test, the rate of return visits and caregivers' satisfaction

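### The variance of 1 behind 75 per group is not tied to the pre-post endpoint and no primary analysis is named; prespecifying adjustment for test 1 settles both at no cost

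*Combined protocol and SAP*

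**What the plan says.** The aim, in the Introduction, is about gain: "The main aim is to compare the gained knowledge between a group of patients informed through the usual procedure" and a group that also sees the video. The endpoint, near the end of Methods, matches it: "The primary efficacy endpoint will be the difference between the score obtained in the initial test and the follow-up test".

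The sample-size paragraph, printed in Methods after the exclusion criteria, sets 80% power and a 5% alpha "to detect a two-tailed difference of 0.5 points between the two groups", allows 15% loss, and concludes: "assuming a 1-point variance in test results based on previous studies[7], this statistical power would be reached by enrolling 75 patients in each group".

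Four design features bear on the point:

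- Test 1 comes before allocation: "They were then randomly assigned to the control or intervention group".
- Both arms are taught the tested content between the tests: "Both sets of instructions explicitly include the information that had been previously asked in the test".
- At follow-up the same caregivers "were asked the same 5 questions from the initial test".
- Allocation is unrestricted: "Simple, 1:1 randomization is performed using R software".

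The protocol has no statistical analysis section. It names no test or model for the primary endpoint and gives neither a variance of the change nor a correlation between the two tests.

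**The concern.** A sample size is tied to an outcome and an analysis, and here neither link is made. The variance of 1 could be read in two ways.

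- **Single-score reading.** It is the variance of one test score. The change between tests then has a different variance, which depends on the pre-post correlation.
- **Change reading.** It is the variance of the change. The calculation then fits the endpoint, and the text only needs to say so.

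The phrase about test results leans towards a single score but does not settle the matter. The correlation is open too. The same caregiver answering the same five questions suggests a positive correlation, while teaching the answers to both arms in between could weaken it.

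A reader therefore cannot tell whether 75 per group gives 80% power for the reported endpoint, or how that endpoint will be analysed. The missing model is a gap under either reading. An unadjusted comparison of change would be unbiased, so what is at stake is precision and a power statement that can be checked.

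**Working it through.** **Inputs from the protocol.** Difference 0.5 points, two-sided alpha 5%, power 80%, variance 1, loss 15%, 75 enrolled per group, 1:1 simple randomisation.

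**Assumptions, because the protocol gives no values.** Pre-post correlation ρ, shown at 0, 0.3, 0.5 and 0.7; equal variance at both tests unless stated otherwise.

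**1. The plan's own figure.** n = 2(1.960 + 0.842)² × 1 / 0.5² = 62.8, so 63 evaluable per group; 63 / 0.85 = 74.1, so 75. This matches, and it shows that 75 requires the analysed outcome to have variance 1.

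**2. Variances.** With variance v₁ at test 1 and v₂ at follow-up:

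- Unadjusted change: v₁ + v₂ − 2ρ√(v₁v₂). With both equal to 1 this is 2(1 − ρ), which equals 1 only at ρ = 0.5.
- Adjusted for test 1: v₂(1 − ρ²). This is the smallest variance of (follow-up − b × test 1) over all b. Setting b = 0 gives the follow-up score and b = 1 gives the change, so the adjusted variance cannot exceed either.
- Change reading with change variance V and equal test variances: v₂ = V / (2(1 − ρ)), so the adjusted variance is V(1 + ρ)/2.

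**3. Power.** Evaluable per group: 75 × 0.85 = 63.75. Noncentrality is 0.5 / (SD × √(2/63.75)), with power from the noncentral t on 125.5 degrees of freedom, or 124.5 when adjusted. For example, at SD = 1 the noncentrality is 0.5 / 0.177 = 2.82 and power is 80%.

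| | ρ = 0 | 0.3 | 0.5 | 0.7 |
|---|---|---|---|---|
| Single-score variance 1, unadjusted change | 51% | 66% | 80% | 95% |
| Single-score variance 1, adjusted | 80% | 84% | 90% | 97.5% |
| Change variance 1, unadjusted change | 80% | 80% | 80% | 80% |
| Change variance 1, adjusted | 98% | 94% | 90% | 86% |

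Under the single-score reading, the unadjusted comparison would need 149, 104, 75 and 45 enrolled per group at these four correlations (normal approximation).

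**4. Simple randomisation.** Under the single-score reading with 127 evaluable in total, averaging over Binomial(127, 0.5) group sizes gives 79.5% adjusted power at ρ = 0. Inflating the error variance by 1 + 1/123 for chance baseline imbalance gives 79.2%, and 82.8% and 89.3% at ρ = 0.3 and 0.5. Hence the wording about 80%.

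**5. Where the floor fails or rises.**

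| Adjusted power | ρ = 0 | 0.3 | 0.5 |
|---|---|---|---|
| Single-score reading, follow-up variance 1.2 | 72.5% | 76% | 84% |
| Single-score reading, loss 20% | 77.5% | 81% | 88% |
| Follow-up variance 0.7, test 1 variance 1 | 92% | 94% | 97% |
| Change reading, change variance 1.2 | 95% | 89% | 84% |

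In the third row, unadjusted change has 57.5%, 73% and 85%. In the last row, adjusted power falls to 79% at ρ = 0.7 and unadjusted change has 72.5% throughout.

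**6. Bounded score.** Simulation used 40,000 trials per setting, N = 127, simple randomisation and integer scores from 0 to 5. Assumed values were latent SD 1, latent means of 3 at test 1 and 4.0 for controls at follow-up, and an observed difference of 0.5. This puts 31% of controls and 56% of the intervention group at the maximum. Adjusted regression kept type I error at 5.0% and interval coverage at 95%. Its power was 91% at ρ = 0 and 93% at observed ρ = 0.31, against 56% and 71% for unadjusted change.

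**The case against.** The plan's arithmetic is correct on its own terms. Since the aim is gained knowledge and the endpoint is the pre-post difference, one can reasonably take the variance to be that of the outcome compared. Unadjusted change then has 80% power at any correlation, and one clarifying phrase would do. The low figures need the single-score reading and a weak correlation; 51% needs a correlation of exactly zero, which is unlikely when the same person answers the same questions. Naming an unadjusted comparison of change would also fill the gap, so adjustment is a gain in efficiency and not the correction of a bias.

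Most of this is right, and it is why the point is one of unverified power and not of a shortfall. It does not remove the concern: the text settles neither the reading nor the correlation, and no model is named under any reading. Adjustment is preferable because it makes the answer insensitive to both unknowns.

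Three smaller points also stand:

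- Under the single-score reading, it is the follow-up variance that must be at most 1. A source figure for test 1 alone, or pooled over both tests, would not establish that.
- The bounded-score simulation supports type I error and coverage, not the 80% floor, because the limit at 5 pulls the follow-up variance below 1.
- In an open-label trial the model counts as prespecified only if fixed before follow-up scores are examined.

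**Conclusion.** The concern holds. The 75 per group is arithmetically right for an outcome with variance 1, but the protocol does not show that the pre-post difference is that outcome, and it names no primary analysis. Under the single-score reading, an unadjusted comparison of change reaches 80% power only at a correlation of 0.5 or more. Under the change reading it reaches 80% regardless.

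Adjusting for test 1 gives about 80% or more under both readings; the lowest figure, allowing for simple randomisation and chance imbalance, is 79.2%. This rests on the relevant variance being at most 1 and loss being at most 15%. The correlation and the separate test variances are assumptions shown as ranges. This should be fixed, but the design itself stands.

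**What to change.** Add a primary analysis statement:

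> Primary analysis: linear regression of the follow-up score (equivalently, of the change from test 1) on randomised group, with the test 1 score as covariate. The group coefficient with its 95% confidence interval is the primary result.

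The group coefficient is identical for either outcome, so the gained-knowledge aim is kept.

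Restate the sample-size sentence, keeping one of the bracketed options:

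> The variance of 1 describes [the follow-up score / the change from test 1], as checked against the cited source. With 75 per group, this variance at most 1 and loss at most 15%, the baseline-adjusted analysis has about 80% power or more to detect 0.5 points.

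Only if it is a single-score variance, add:

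> An unadjusted comparison of change would have 51%, 66%, 80% and 95% power at a pre-post correlation of 0, 0.3, 0.5 and 0.7, assuming equal variances at both tests.

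If it is the change variance, leave that last sentence out and put no cap on the follow-up variance: at a correlation of 0.7 the follow-up variance would be 1/(2 × 0.3) = 1.67. If the source gives only a test 1 or pooled variance, state the follow-up variance as an assumption.

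The cost is wording only, with no new data and no extra patients. The change should go through the ethics-committee route that the protocol sets for modifications, before any follow-up scores are examined.

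### The talk common to both arms is given after allocation in an open-label trial; opening the envelope after the talk would cheaply close one route for bias

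*Combined protocol and SAP*

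**What the plan says.** The Introduction frames the question as the effect of "adding a set of video discharge instructions to the usual verbal information given at discharge". It states the expected result in advance: by "associating video discharge instructions to usual verbal instructions, the comprehension will be better and the satisfaction with the information received will be higher".

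The sequence is in the Methods text printed under Exclusion criteria. Caregivers take test 1 before discharge; "They were then randomly assigned to the control or intervention group"; the instructions are then described arm by arm. Controls receive the verbal information, which follows a Spanish society's guidelines. In the other arm, "patients will be shown a short 2-minute video providing the same information about AGE, in addition to verbal instructions". Whether the video comes before or after the talk is not stated.

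The plan contains safeguards for the talk. "In both groups, instructions will be given by one of the main investigators in order to provide homogeneous and consistent information". On content, "Both sets of instructions explicitly include the information that had been previously asked in the test". On written material, "All patients additionally received a discharge report which includes instructions concerning aftercare treatment".

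The same section describes allocation and masking. "Simple, 1:1 randomization is performed using R software", and assignment is made by opening numbered envelopes in sequence. The trial is declared open-label on the ground that the interventions cannot be masked. The primary endpoint is the change in score from test 1 to the telephone follow-up, which repeats the same 5 questions. Satisfaction with the information, scored 0-10, is secondary.

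**The concern.** The comparison isolates the video only if the verbal part is the same in both arms. Under the stated order, a main investigator may know the arm while giving the talk. That talk covers the very items on which the primary endpoint is scored.

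The direction of any bias is open. A speaker who knows that a video will follow may shorten the talk, which would dilute the video effect. A speaker who shares the stated hypothesis may be more thorough in the video arm, or briefer with controls, which would inflate it.

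Because the video carries the same information, an item dropped from the talk in that arm would still reach the caregiver. What could differ is repetition and emphasis. The plan does not record the content or length of individual talks, so the analysis could not separate a talk effect from a video effect. The satisfaction score is open to the same influence.

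**Working it through.** **Order of events.** Test 1 comes first, assignment second and instructions third. The talk is common to both arms, so it could be given before assignment, but the plan places it after. The reason given for the open-label design applies to the video. It does not apply to a talk given while the envelope is still closed.

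**What the safeguards cover.** Using main investigators limits differences between speakers, but not differences by arm within a speaker who knows the arm. The guideline basis and the required coverage of tested items govern content, not time or emphasis. The discharge report goes to everyone. No script, checklist or fidelity check is described.

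**The plan's sample size, reproduced.** The inputs, all from the sample-size paragraph under Exclusion criteria, are a difference of 0.5, variance 1 (SD 1), two-sided alpha 5%, power 80% and loss 15%.

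- n per group = 2 × (1.960 + 0.842)² × 1² / 0.5² = 62.8, rounded up to 63.
- 63 / (1 − 0.15) = 74.1, rounded up to 75, which matches the plan. The t-test version gives 64 and then 76.

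**Illustration of scale.** The documents give no size for a difference in the talk, so the shifts s below are assumed. They are 0.05, 0.1 and 0.2 points, or 10%, 20% and 40% of the 0.5-point target.

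- Evaluable per arm: 75 × 0.85 = 63.75.
- SE = √(2 × 1² / 63.75) = 0.1771, taking SD 1 for the change score (an assumption; the plan states the variance for test results).
- No true effect: P(favours the arm helped by the shift) = 1 − Φ(1.960 − s/SE); P(favours the other arm) = Φ(−1.960 − s/SE).
- True effect 0.5: power = Φ((0.5 ± s)/SE − 1.960).
- Coverage of the 95% confidence interval = Φ(1.960 − s/SE) − Φ(−1.960 − s/SE).

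| Assumed shift s | No effect: favours helped arm | No effect: favours other arm | No effect: total rejection | Power, shift towards control | Power, shift towards video | Coverage |
|---|---|---|---|---|---|---|
| 0 | 2.5% | 2.5% | 5.0% | 80.6% | 80.6% | 95.0% |
| 0.05 | 4.7% | 1.2% | 5.9% | 71.9% | 87.4% | 94.1% |
| 0.1 | 8.1% | 0.6% | 8.7% | 61.7% | 92.3% | 91.3% |
| 0.2 | 20.3% | 0.1% | 20.4% | 39.5% | 97.7% | 79.6% |

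With a true effect of 0.5, the expected estimate is 0.45, 0.40 or 0.30 if the shift favours control, and 0.55, 0.60 or 0.70 if it favours the video. The higher power in the second case comes only from overstating the effect.

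**The case against.** Randomising after baseline and then delivering the arm's instructions is an ordinary open-label sequence, and no document shows that the talk would differ. Consistency between groups is the declared purpose of using main investigators, and the planned content is specified. **This stands in part.** It is why the point is a possible improvement and not a demonstrated bias. But the stated purpose has no mechanism behind it that equalises time and emphasis.

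The assumed shifts have no source, and the largest is demanding. On a 5-question test with one point per question, a mean shift of 0.2 equals one caregiver in five gaining a whole extra correct answer from emphasis alone. **This stands.** The 0.2 row should be read as an upper illustration.

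On a pragmatic reading, any natural adjustment of the talk belongs to the video strategy. **This is weak here.** The Introduction, the aims and the ethics section all describe a video added to the usual talk, and the plan asks for homogeneous instructions in both groups.

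The remedy is partial, because the unmasked telephone call produces the primary outcome itself. It also fixes the video as the later component, and the protocol requires ethics committee acceptance of any modification. **All of this is true.** None of it is a reason to leave an inexpensive route open.

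**Conclusion.** The point holds as a low-cost improvement to consider. The plan allocates before giving the information common to both arms, the trial is open-label, and nothing keeps the speaker unaware of the arm. A difference in the talk could therefore enter the primary comparison directly.

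Its existence, sign and size cannot be settled from the documents. Under the assumed shifts of 0.05 to 0.2 points, two-sided rejection under no true effect would be 5.9% to 20.4% instead of 5%. Interval coverage would be 94.1% to 79.6%. Power at a true 0.5 would be 71.9% to 39.5% if the shift favours control. These figures rest on the normal approximation, 63.75 evaluable per arm and SD 1 for the change score. The stated 75 per group is not in dispute.

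**What to change.** State the order in the Methods: test 1; verbal information to every caregiver; open the next envelope; show the 2-minute video to those allocated to it, with no further explanation that depends on the arm; discharge. The envelope must stay closed until the talk ends. Under simple randomisation, earlier assignments do not reveal the next one, so the speaker would not know the arm during the talk. This would weaken late in enrolment if exactly 75 per group were enforced.

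A short checklist of the tested items, completed for every talk, could be added. Alone it would control content but not emphasis.

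The cost is one sentence in the protocol, plus the ethics committee acceptance that any modification needs. The 75 per group, the endpoint and the staffing are unchanged. The small downside is that the video would always follow the talk, so a video-first format, which the plan now leaves open, is ruled out. Questions answered after the envelope is opened and the open-label telephone follow-up would remain possible sources of bias.

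### The reason given for open-label conduct does not reach the follow-up caller or the marker, and nothing in the plan keeps the arm from them

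*Combined protocol and SAP*

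**What the plan says.** All of this stands in the Methods, in the text that follows the Exclusion criteria, unless another place is named.

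- **Masking.** "The trial will be open-label because of the characteristics of the interventions, which do not make masking possible". No other reason is given.
- **Follow-up test.** After discharge, "all caregivers will be contacted by telephone and were asked the same 5 questions from the initial test". On timing: "The first telephonic contact will be established 72 hours after discharge". On the respondent: "The questionnaire must be completed by the same caregiver as in Step 1".
- **Callers.** They are identified only in passing: "If investigators are not able to contact them at first, telephonic contact will be repeated every 1-2 days". No one is named as marking the answers.
- **Outcomes that use the call.** "The primary efficacy endpoint will be the difference between the score obtained in the initial test and the follow-up test". A secondary assessment is "the number of caregivers who get a 5-point score in the follow-up test".
- **Partial safeguards.** All questions "will be asked to all patients independently of the group they are allocated to". The instructions in both arms are also said to cover the content of the test.
- **Other roles.** Four investigators enrol, and one of the main investigators gives the instructions in both groups.
- **Data.** Under Data confidentiality, the main investigators keep a registry linked to study numbers, partly for follow-up, and the data go into an Excel file. The text does not say whether either shows the arm.

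**The concern.** The plan treats the whole trial as impossible to mask, on a ground that applies to only part of it. A caregiver knows whether a video was shown, and so does the investigator who was in the room. A person who telephones days later, or who marks five recorded answers, need not know.

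The follow-up score is obtained in live conversation, and the study hypothesis favours the video. If the caller or marker knows the arm, a hint on the telephone or a generous reading of an answer could add points in the video arm. A positive result would then be harder to separate from that bias. How much room there is depends on the format of the five items, which the document does not give. Closed items with a fixed key would leave little; free spoken answers would leave more.

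**Working it through.** **1. Whom the stated reason covers**

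| Role | Who, according to the plan | Does the nature of the intervention rule out masking? |
|---|---|---|
| Caregiver | Sees the video or does not | Yes |
| Instructor | One of the main investigators | Yes |
| Caller | Investigators, not further specified | No |
| Marker | Not named | No |

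No text separates the caller or marker from those who enrol or instruct, or restricts access to the allocation. The sequentially numbered envelopes conceal the arm only until assignment.

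**2. The plan's own sample size**

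Inputs from the sample size paragraph: difference 0.5 points, variance 1 (SD 1.0), two-sided alpha 5%, power 80%, loss 15%.

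n = 2 × (1.960 + 0.842)² × 1.0² / 0.5² = 62.8, so 63 per arm. Then 63 / 0.85 = 74.1, so 75 per arm, as planned. An SD of 1.0 for the change score therefore fits the stated size.

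The text does not say whether the variance of 1 belongs to a single test or to the change. If it belongs to a single test, the SD of the change is √(2(1 − ρ)), where ρ is the correlation between the two tests. Assumed values of ρ = 0, 0.5 and 0.7 give SDs of 1.41, 1.0 and 0.77.

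**3. Effect of an assumed bias when the video has no true effect**

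Evaluable per arm: 75 × 0.85 = 63.75. SE = SD × √(2/63.75), which is 0.177 at SD 1.0. The smallest significant difference is 1.96 × SE. The error rate is P(|Z + b/SE| > 1.96), where b is a constant shift in favour of the video arm. The values of b are assumptions; the document offers no basis for choosing one.

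| SD of change | Smallest significant difference | b = 0.05 | b = 0.1 | b = 0.2 |
|---|---|---|---|---|
| 0.77 | 0.27 | 6.5% | 11.3% | 30.8% |
| 1.0 | 0.35 | 5.9% | 8.7% | 20.4% |
| 1.41 | 0.49 | 5.5% | 6.8% | 12.6% |

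At one point per question, these biases equal b × 63.75 = 3.2, 6.4 and 12.8 extra credited answers in the video arm. That is about 1%, 2% and 4% of the 5 × 63.75 = 318.75 answers.

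**4. Effect on an observed difference of 0.5 (estimate less b, with 95% CI)**

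- SD 1.0: less 0.1 is 0.40 (0.05 to 0.75), still significant; less 0.2 is 0.30 (−0.05 to 0.65), not significant.
- SD 1.41: less 0.05 is 0.45 (−0.04 to 0.94), already not significant.
- SD 0.77: less 0.2 is 0.30 (0.03 to 0.57), still significant.

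**The case against.** The strongest reply is that this is a small single-centre trial that openly declares itself open-label, and that its test leaves little room for discretion. The same five questions are put to both arms. Five questions and a 5-point score suggest one point each. Instructions in both arms cover the tested content, which points to factual items with answers settled in advance. The bias sizes above are assumed, so they show what a bias would do and not that one is likely.

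Much of this stands. The safeguards are real and narrow the scope for discretionary marking, and the illustration should not be used to raise the seriousness of the point. But the safeguards fix what is asked and taught, not how an answer is drawn out, so prompting remains possible. They also do not establish closed items or a written key. Declaring a trial open-label discloses the lack of masking; it does not explain why the assessor must be unmasked.

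A reader might also infer that the baseline score is equally exposed. The document does not support that. Participants fill in test 1 themselves and are randomised afterwards, so no one can prompt by arm at that stage. Only later marking is open, which is minor and largely dealt with by one fixed key.

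**Conclusion.** The point holds as a gap in the design that should be closed. As written, an investigator who knows the arm may elicit and mark the primary outcome, and the only reason given for not masking does not apply to that task. If callers and markers are already kept from the arm, a sentence saying so would settle it.

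Two stronger readings should be resisted. A reader might infer that callers will know the arm, or that the result will be biased. The document says neither; it only fails to prevent it. A reader might also infer a general rule on whether a small bias would overturn a result at the 0.5-point target. There is none: the answer changes with the SD of the change score, which the document does not fix beyond doubt.

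The size is illustrative. A bias of 0.2 points with no true effect gives an error rate between 12.6% and 30.8% over the SDs considered. This assumes a constant shift, a normal approximation and exactly 15% loss in each arm.

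**What to change.** Describe the trial as open-label with a masked outcome assessor where feasible, and add three provisions:

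1. **Caller.** An existing investigator who neither enrolled nor instructed that family makes the call, from a list without the arm. The list can carry the study number, telephone number, the caregiver who took test 1 and the due date, so that the same-caregiver and 72-hour rules can still be checked. The caller should have no access to allocation in the registry or Excel file. If no such investigator is free, use a fixed script without prompts, record answers verbatim, and have another existing investigator mark them without the arm.
2. **Order.** Ask the five knowledge questions first and the question on the usefulness of video last, because that question invites the caregiver to reveal the arm.
3. **Key.** Mark both tests against one fixed answer key.

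Recording after the call whether the caller learned the arm is a useful optional extra.

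**Cost.** The sample size does not change. The work is a call rota, a list and a key. If recruitment is even over the planned 12 months, which is an assumption, first calls number 150 / 52 = 2.9 per week, plus repeats. Up to three enrolments per shift are allowed, so calls may cluster. Whether existing staff suffice is unknown: the plan gives four investigators for enrolment but not how many instruct.

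**Limits.** Some caregivers will reveal the arm by remarks, the fallback protects marking but not prompting, and satisfaction is still rated by unmasked caregivers.
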